9.3.2 Evaluable Population

The Evaluable Population is defined as all patients who undergo PAE with Embosphere Microspheres, have valid IPSS data for the 12 month time point, and do not have any major protocol violations.

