9.5 Efficacy Analyses

All efficacy analyses will be based on the ITT Population on the locked database after all patients have completed the 12 month follow-up visit or are lost to follow-up. If <15% of patients are excluded from the Evaluable Population, only the analyses of the ITT Population will be presented in the summary tables. If >15% of patients are excluded from the Evaluable Population, secondary efficacy analyses of the primary efficacy outcome will be performed on the Evaluable Population and included in the summary tables.

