9.5.1 International Prostate Symptom Score (IPSS)

The primary efficacy outcome will be based on the IPSS. The IPSS is a frequent used, validated, 8 item (7 symptom burden questions and 1 quality of life question) instrument which can be serially performed to compare the progression of symptoms and their severity over months and years. Patients are asked to assess how often they have experienced the following 7 symptoms in the past month: incomplete emptying, frequency, intermittency, urgency, weak urine stream, straining and nocturia. The response categories range from 0=Not at all to 5=Almost always. The total IPSS score is calculated by summing the responses for the 7 symptom burden items. The eighth item is an assessment of patient quality of life due to LUTS and does not contribute to the IPSS score calculation.

Patients will be classified into one of 3 symptom severity categories based on their total IPSS score as follows:

- Mildly symptomatic: 0-7
- Moderately symptomatic: 8-19
- Severely symptomatic: 20-35

The IPSS total score will be summarized for the baseline, 1 month, 6 month and 12 month time points, including change from baseline. Change from baseline will be calculated as post baseline IPSS score minus baseline IPSS score. A negative value indicates symptom improvement. 95% confidence intervals will be calculated for the mean change from baseline to the post baseline time points. For informational purposes, IPSS scores will also be summarized separately for patients that receive unilateral and bilateral PAE if there are sufficient numbers in both groups.

The primary efficacy analysis will be the change in IPSS total score from baseline to 12 months post PAE for the ITT population. A Paired-Sample Wilcoxon Signed Rank Test will be used to assess the statistical significance of the change from baseline to 12 months post PAE. A secondary analysis of the proportion of patients who have improved by at least one IPSS symptom category (i.e., severe to moderate, severe to mild, or moderate to mild) from baseline to 12 months post PAE will also be performed. A 95% confidence interval will be calculated for the proportion. The proportion of patients improving at least 3 points on the IPSS total score at the 12 month time point will also be summarized and the corresponding 95% confidence interval will be calculated.

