9.5.7 Handling of Missing and Spurious Efficacy Data

All available data for treated patients will be included in the by-patient data listings and summary tables.

Obvious outliers for continuous data will be investigated and data queries will be generated as appropriate. If an outlier is determined to be a valid response, the summary analyses may be performed both including and excluding the outlier in order to evaluate the impact on the summary statistics. All outliers impacting the summary analyses will be discussed in the study report.

In the ITT analyses for the IPSS, IIEF, PSA and uroflowmetry variables, a Last Observation Carried Forward (LOCF) approach will be used. If a patient does not have any valid post-baseline data for a given outcome, the baseline value will be carried forward. This approach conservatively assumes there has been no improvement for those patients with completely missing post-baseline data. In addition, sensitivity analyses will be performed to determine the robustness of the ITT results using multiple imputation techniques if the data are determined to be missing at random.

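### LOCF fills missing 12-month IPSS scores in the single-arm primary analysis, and neither planned check addresses informative dropout

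*Combined protocol and SAP*

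**What the plan says.** Section 9.5.1 defines the primary analysis: "The primary efficacy analysis will be the change in IPSS total score from baseline to 12 months post PAE for the ITT population". It is tested with a paired Wilcoxon signed-rank test. Two responder proportions at 12 months accompany it: improvement by at least one severity category, and a 3-point criterion ("The proportion of patients improving at least 3 points on the IPSS total score at the 12 month time point will also be summarized").

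Section 9.5.7 sets the missing-data rule: "In the ITT analyses for the IPSS, IIEF, PSA and uroflowmetry variables, a Last Observation Carried Forward (LOCF) approach will be used". Baseline is carried forward only for a patient with no valid post-baseline value, and the claim of conservatism is confined to that case: "This approach conservatively assumes there has been no improvement for those patients with completely missing post-baseline data".

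Two checks are planned:

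- Section 9.5.7 provides sensitivity analyses "using multiple imputation techniques if the data are determined to be missing at random".
- Section 9.3.2 defines an Evaluable Population of treated patients who "have valid IPSS data for the 12 month time point, and do not have any major protocol violations". Section 9.5 says when it is used: "If <15% of patients are excluded from the Evaluable Population, only the analyses of the ITT Population will be presented in the summary tables", and "If >15% of patients are excluded from the Evaluable Population, secondary efficacy analyses of the primary efficacy outcome will be performed on the Evaluable Population".

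Section 4 describes one treatment arm of 20 patients. Section 5.3 provides for remote IPSS and IIEF collection from patients who do not return, and section 6 asks withdrawn patients to complete the 12-month evaluations where possible.

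**The concern.** A patient who has a month-1 or month-6 score but no month-12 score enters the primary analysis with the earlier score. If he improved, relapsed and then left, LOCF credits him with a gain he no longer has. If he left before improving, LOCF withholds a gain he later had. The direction is not known in advance, and with no control arm nothing offsets the error.

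The planned checks do not fill the gap. Observed data cannot show that scores are missing at random, and if dropout is judged informative the imputation analysis is not run at all. The Evaluable analysis requires a 12-month score, so it leaves out the patients in question. Section 9 contains no failure imputation for patients with some follow-up, no delta adjustment and no tipping-point analysis.

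At stake are the size of the mean change and the responder proportions, which are what a reader takes from an uncontrolled study of 20 patients.

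**Working it through.** The plan states no dropout rate, SD or expected effect, and section 9.2 says no sample size calculation was made, so there is no planned figure to reproduce. Everything below is illustrative.

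**Inputs.** From the documents: 20 patients (section 4); a 6.7-point improvement in clinical severity score in a 15-patient series, and clinical success of 81.9% at 1 month and 75.2% at 1 year in a 255-patient series (both in the background section). Assumed: that the 6.7 points apply to IPSS, and a two-sided 0.05 level for the signed-rank test, since the plan states none.

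**1. The 15% rule with 20 treated.** Exclusions/20: 1 = 5.0%, 2 = 10.0%, 3 = 15.0%, 4 = 20.0%. One or two: ITT only. Four: Evaluable analysis added. Exactly three: neither rule applies.

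**2. Shift in the mean.** Overstatement = (k/20) × (carried gain − true gain). Maximum inflation of the 3-point responder proportion = k/20.

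| k missing | Carried 6.7, true 0 | Carried 6.7, true 3 | Maximum responder inflation |
|---|---|---|---|
| 1 | 0.335 | 0.185 | 5 points |
| 2 | 0.67 | 0.37 | 10 points |
| 3 | 1.005 | 0.555 | 15 points |
| 4 | 1.34 | 0.74 | 20 points |

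The error is the same size in the other direction: a patient carried at no gain who truly reached 6.7 gives 6.7/20 = 0.335 points of understatement.

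**3. A milder case from the cited series.** If four dropouts followed only the average decline, carrying month 1 forward would add (4/20) × (81.9 − 75.2) = 1.34 percentage points to the success rate. If all four had failed by 12 months, it would add (4/20) × 81.9 = 16.4.

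**4. Worked example with four missing.** Assume 16 observed changes: −14, −12, −11, −10, −9, −8, −7, −6, −5, −4, −3, −2, 1, 2, 4, 6. CIs are t-based.

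| Analysis | Mean change (95% CI) | Improved by ≥3 |
|---|---|---|
| LOCF, four carried at −7 | −5.30 (−7.79 to −2.81) | 15/20 (75%) |
| Evaluable, four omitted | −4.875 (−8.02 to −1.73) | 11/16 (69%) |
| Four truly at 0 | −3.90 (−6.53 to −1.27) | 11/20 (55%) |

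The Evaluable analysis would be reported here and would show a discrepancy, but it does not recover the last row. In the opposite case, four carried at −2 who truly reached −7, LOCF gives −4.30 and 11/20 instead of −5.30 and 15/20.

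**5. Tipping point in the same example.** With all four set to +3, the signed-rank p is 0.038; at +4 it is 0.054, while the CI (−6.09 to −0.11) still excludes 0. At +5 the CI is −6.00 to 0.20. The planned test therefore tips one step before the CI. Setting the four to zero leaves p at 0.009, the same as for the 16 alone, because the standard signed-rank test drops zeros.

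**6. Effect on the test.** Simulation with 3,000 runs, n = 20 and changes drawn from Normal(−6.7, SD) and rounded; for the truth, k patients are reset to 0. Rejection under LOCF versus truth: SD 7, k = 2, 98% versus 96%; SD 7, k = 4, 98% versus 95%; SD 9, k = 4, 88% versus 79%. At SD 7 and k = 4 the mean is −6.75 versus −5.40, and responders are 73% versus 58%.

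**The case against.** The strongest reply is that the problem is small and partly handled. Remote questionnaires and the request to withdrawn patients target exactly these scores, and the by-patient listings would let a reader recalculate a zero-change result for one or two patients. With four missing, the Evaluable analysis is already triggered. The 20-point responder shift needs all four to be responders who relapse fully; average decline in the cited series gives about 1.3 points. The 6.7-point figure comes from a small series treated with nonspherical PVA particles, not the study device. All of this stands, and it limits the size of the point. It does not supply an analysis that allows for informative dropout.

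A reader might infer that LOCF necessarily flatters the treatment, or that the finding of improvement is at risk. The documents support neither: the bias can run both ways, and in the example the four missing patients must all worsen by 4 points before the planned test loses significance. Nor does the plan call LOCF conservative in general; that claim covers only patients with no follow-up score.

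A reader might also expect unconditional multiple imputation to cure the problem. Standard multiple imputation itself assumes missing at random, so it would not.

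The 15% gap is a drafting slip. It arises only with exactly 3 exclusions from exactly 20 treated; 3 of 19 is 15.8% and triggers the Evaluable analysis.

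**Conclusion.** The concern holds, at modest size. The primary analysis relies on LOCF for patients with some follow-up but no 12-month score, and no planned analysis addresses informative dropout. With one or two of 20 missing and no other exclusions, LOCF is the only planned result unless the data are declared missing at random. The mean improvement could then be overstated by 0.34 to 0.67 points and the 3-point responder proportion by up to 5 to 10 percentage points. With four missing, the figures could reach 1.34 points and 20 percentage points, but the Evaluable result would stand beside LOCF.

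These figures assume a 6.7-point carried gain and full return to baseline. The effect estimate and responder proportions are exposed; the conclusion that symptoms improved is unlikely to change. The IIEF aspect is marginal: carrying baseline forward assumes no decline in an outcome where decline is the harm of interest, but it matters only for a patient with no follow-up IIEF at all.

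**What to change.** Keep LOCF and the signed-rank test as the primary analysis. Before database lock, amend section 9 as follows.

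1. Whenever any 12-month IPSS is missing, report a sensitivity analysis that sets those patients to zero change and non-responder. Show it on the mean change with 95% CI and on both responder proportions; the signed-rank p-value alone would not register the added zeros. Add a tipping-point analysis that shifts the missing changes in 1-point steps and reports both where the signed-rank test loses significance and where the CI first includes 0. State the significance level used.
2. In section 9.5, make the trigger 15% or more, or report the Evaluable analysis whenever anyone is excluded.
3. Optional: run multiple imputation without the precondition, labelled as a missing-at-random check only and naming the imputation variables (for example baseline, month-1 and month-6 IPSS). Also report observed IIEF subscales without carry-forward.

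The cost is SAP wording and a little more analysis, with no new data, visits or patients. Some results may look slightly less favourable, and multiple imputation in about 20 patients will be imprecise.

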2.2 Secondary Objectives

The secondary objectives of this investigation are to assess the following outcomes, compared to baseline values when appropriate:

1. PAE-related adverse events
2. Overall adverse events
3. Prostate volume as determined by transrectal ultrasound
4. Serum prostate specific antigen (PSA) level
5. Post void residual volume (PVR) as determined by transabdominal ultrasound
6. Post void residual urinary volume (PVR) as determined by uroflowmetry
7. Peak urine flow rate (Qmax) as determined by uroflowmetry
8. Sexual function as determined by the International Index of Erectile Function (IIEF)

3. Patient Population

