- For PAE: Hematospermia, hemorrhage, injury to the bladder (including the bladder neck, ureteral orifice or trigone), impact on future fertility, vasospasm, rectorrhagia, inguinal hematoma, bladder/bladder neck ischemia and necrosis leading to bladder resection, balanitis, erectile dysfunction, rectal ischemia, rectal injury, allergic reaction to Embosphere Microspheres or contrast agent, radiation exposure, vascular perforation, need for subsequent surgery to repair non-target ischemia, and sensory abnormality

Serious Adverse Event: A serious adverse event (SAE) is any adverse event, occurring at any dose and regardless of causality that:

- Results in death
- Is life-threatening, such that the patient was at immediate risk of death from the event as it occurred (i.e., it does not include a reaction which hypothetically might have caused death had it occurred in a more severe form)
- Requires inpatient hospitalization or prolongation of existing hospitalization. Hospital admissions and/or surgical operations scheduled to occur during the study period but planned prior to study entry are not considered AEs if the illness or disease existed before the patient was enrolled in the study, provided that the patient's condition does not deteriorate in an unexpected manner during the study (e.g., surgical procedure performed earlier than planned)
- Results in persistent or significant disability/incapacity, such that the patient experiences a substantial disruption of their ability to conduct normal life functions

- Is an important medical event as determined by the Investigator. An important medical event is an event that may not result in death, be life-threatening, or require hospitalization, but may be considered an SAE when, based upon appropriate medical judgment, it may jeopardize the patient and may require medical or surgical intervention to prevent one of the outcomes listed above. Examples of such medical events include allergic bronchospasm requiring intensive treatment in an emergency room or at home, blood dyscrasias or convulsions that do not result in inpatient hospitalization, or the development of drug dependency or drug abuse.

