9.2 Sample Size Calculations

This is a phase I/II, single center, prospective, single arm, investigational study to evaluate the safety and efficacy of prostate artery embolization (PAE) for treatment of severe LUTS related to BPH in patients with prostate size between 40 and 300 cm³ that have either failed or are intolerant to medical management. Twenty patients treated with PAE with Embosphere Microspheres are considered sufficient to provide data that will be used to evaluate the study objectives. No formal sample size calculations have been performed.

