9.5.5 International Index of Erectile Function (IIEF)

The IIEF is a commonly used, validated instrument that consists of 15 items. Five subscales are calculated as follows:

- Erectile function (items 1-5, 15)
- Orgasmic function (9, 10)
- Sexual desire (11, 12)
- Intercourse satisfaction (6-8)
- Overall satisfaction (13, 14)

Each subscale will be summarized separately for the baseline, 1 month, 6 month and 12 month time points, including change from baseline. Change from baseline will be calculated as post baseline IIEF score minus baseline IIEF score. Positive values indicate an improvement in sexual function. 95% confidence intervals will be calculated for the mean change from baseline for each time point.

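### Carrying the baseline IIEF forward is justified as conservative, but for loss of sexual function a zero change is the favourable assumption: it shrinks the reported loss and usually narrows its interval

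*Combined protocol and SAP*

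**What the plan says.** Section 9.5 bases every efficacy analysis on the ITT population, which section 9.3.1 defines as all men who undergo PAE. For missing values, section 9.5.7 says: "In the ITT analyses for the IPSS, IIEF, PSA and uroflowmetry variables, a Last Observation Carried Forward (LOCF) approach will be used". A man with nothing valid after baseline on an outcome is given his baseline value. The justification is: "This approach conservatively assumes there has been no improvement for those patients with completely missing post-baseline data". The IIEF is not excepted. The same section adds multiple imputation as a sensitivity analysis, on condition that the data are judged missing at random.

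The IIEF is the instrument for secondary objective 8 (section 2.2). Section 9.5.5 reports the change in each of five subscales and fixes the direction: "Positive values indicate an improvement in sexual function". It also says: "95% confidence intervals will be calculated for the mean change from baseline for each time point". No test is planned. Section 7.1 lists among the possible adverse events of PAE "balanitis, erectile dysfunction, rectal ischemia, rectal injury", and Appendix C repeats the list.

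On size, section 9.2 says "No formal sample size calculations have been performed". It offers no SD, effect size or expected dropout. Section 6 says that withdrawn patients are not replaced.

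**The concern.** Whether an imputed value is conservative depends on the direction in which the outcome has to be guarded. For symptom score, flow rate and residual volume the claim to be guarded against is benefit, so no change works against the treatment. For sexual function the question is mainly whether men lose function. A man who never returns a questionnaire is entered as unharmed, which works in the treatment's favour.

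Two things follow. The mean loss is pulled towards zero. The imputed zeros also count as observations, so n goes up and, unless the loss is large, the SD goes down. The interval then claims more precision than the questionnaires provide. With 20 men and no replacement, each imputed man is 5% of the result. What is at stake is the size of any loss reported for secondary objective 8, and how far down its interval reaches.

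**Working it through.** The plan states no figure for the IIEF, so there is nothing to reproduce. The check asks what the stated rule does to a mean and its 95% t-interval.

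**Inputs.** N = 20 (section 9.2). Assumed, because the documents give none: SD of change s = 6 points on the erectile function domain (items 1–5 and 15, maximum 30); k men with no IIEF after baseline; r = N − k men observed, with mean change m.

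**Formulas.**
- Observed data: m ± t(r−1) × s/√r.
- With k zeros added: mean = m × r/N; sum of squares SS = (r−1)s² + (r × k/N)m²; half-width = t(19) × √(SS/19/20), where t(19) = 2.093.

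**Observed mean 0** (SS = (r−1) × 36):

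| k | Half-width, observed data | SS | Half-width, zeros added | Ratio |
|---|---|---|---|---|
| 1 | 2.89 | 648 | 2.73 | 0.95 |
| 2 | 2.98 | 612 | 2.66 | 0.89 |
| 4 | 3.20 | 540 | 2.50 | 0.78 |

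With all 20 men observed at the same SD, the half-width would be 2.093 × 6/√20 = 2.81. The imputed intervals are narrower than if nobody were missing.

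**Observed mean −4, k = 4.**
- Observed data: −4 ± 3.20, that is −7.2 to −0.8.
- Zeros added: mean −4 × 16/20 = −3.2; SS = 540 + 3.2 × 16 = 591.2; half-width 2.61; interval −5.8 to −0.6.

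**Where the narrowing ends.** Setting the two half-widths equal and solving for |m|/s gives about 1.5 at k = 1, 1.7 at k = 4 and 1.9 at k = 6. Beyond that, the zeros widen the interval.

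**Coverage** (20,000 simulated trials, normal changes, true change −0.5 SD, k = 4; informative dropout means weights exp(−0.8 × change in SD units), so worse men are likelier to be missing):

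| Missingness | Mean, zeros added | Coverage, zeros added | Mean, observed data | Coverage, observed data |
|---|---|---|---|---|
| Completely at random | −0.40 | 92% | −0.50 | 95% |
| Informative | −0.27 | 78% | −0.34 | about 90% |

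At k = 2, coverage with zeros added is about 95% and 91%. If the true change is zero and data are missing completely at random, coverage stays at about 95%, because the imputed value is then right on average.

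**Why observed data alone are not enough.** Suppose 16 men average −2 and 4 missing men each lost 10. The true mean is (16 × −2 + 4 × −10)/20 = −3.6. The plan reports −32/20 = −1.6, and observed data give −2.0. Dropping the imputation recovers 0.4 of the 2.0-point gap. The other 1.6 comes from who is missing.

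**LOCF for men with some follow-up** (4 of 20 missing at month 12, half carrying month 1 and half month 6, correlation 0.6 between visits). If loss progresses, a true −0.80 SD is reported as −0.71. If loss is flat, −0.50 is reported as −0.50. If function recovers, −0.20 is reported as −0.28. The half-width is 0.46 to 0.47 SD in all three, against 0.52 from observed data.

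**The case against.** A fair defence has five parts.

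1. **LOCF is not a no-change assumption.** It carries forward any loss already recorded, and the plan attaches the word conservative only to men with nothing after baseline. This stands. A reader might infer that the whole LOCF rule favours PAE. The documents do not support that, because the direction depends on whether loss progresses, holds or recovers. What remains against LOCF is that it treats imputed values as observed.
2. **Few men will be affected.** There is a visit at 1 month, and section 5.3 allows the IIEF to be collected by telephone, email or mail. This also stands. Four men out of 20 is an illustration, not a forecast.
3. **Multiple imputation is planned.** This stands in part. It depends on the data being judged missing at random, which observed data cannot establish. It therefore leaves out the case that matters most, dropout because function was lost. The Evaluable Population analysis does not fill the gap: section 9.5 limits it to the primary outcome, and only when more than 15% are excluded.
4. **Harm is recorded elsewhere.** Erectile dysfunction reported as an adverse event is counted under section 9.6.1 without imputation, and listings, minima and maxima will show individual losses. This is true for men who were seen. The remote contact in section 5.3 covers questionnaires and new treatments, not adverse events, so a man lost to follow-up would tend to look event-free there too.
5. **Nothing is wrongly excluded.** A reader might infer that the interval will rule out a clinically relevant loss that really occurred. The plan sets no threshold for a relevant loss and no IIEF test, so this cannot be shown. In the −4 example the interval still reaches −5.8.

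**Conclusion.** The point holds for baseline carried forward on the IIEF. The stated justification has the wrong sign for an outcome on which harm is expected to appear. The rule reduces the reported mean loss by exactly k/20 relative to the observed mean, and it narrows the interval unless the loss exceeds about 1.5 to 1.9 SD. Under the assumed SD of 6 and an observed mean of 0, the narrowing is about 5% for one man, 11% for two and 22% for four. With an observed mean of −4 and four such men, the report becomes −3.2 and the lower limit moves from −7.2 to −5.8.

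The SD, the mean changes and the number of missing men are all assumptions. With one or two men affected, the distortion is modest. It should not be read as a bias of known direction in LOCF as a whole, nor as undercoverage in every case: with no true change and data missing completely at random, coverage is unaffected. The point concerns a secondary, untested outcome and does not touch the primary IPSS analysis.

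**What to change.** - In section 9.5.7, remove the IIEF from the LOCF and baseline-carried-forward rule.
- In section 9.5.5, analyse each IIEF domain on observed data with n shown at every visit, or fit a repeated-measures model to all visits.
- Pre-specify one sensitivity analysis for men without IIEF data, not conditional on missing at random. It could assign an unfavourable value (for example the worst fall observed) or subtract a stated range of deltas from imputed values. This is needed because observed-data analysis is also biased if harmed men drop out.
- State that the conservative rationale does not apply to the IIEF. It can stay for IPSS, Qmax and PVR.

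The cost is a few lines of SAP text, a small extra table and a slightly wider interval for the IIEF. No extra data collection is needed.
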